8.3.2.2 RELATIONSHIP TO STUDY INTERVENTION

Using the investigator clinical judgment, the relation of the adverse events to the use of the device will be reported as,

• **Definitely Related** – There is clear evidence to suggest a causal relationship, and other possible contributing factors can be ruled out. The clinical event, including an abnormal laboratory test result, occurs in a plausible time relationship to study intervention administration and cannot be explained by concurrent disease or other drugs or

chemicals. The response to withdrawal of the study intervention (dechallenge) should be clinically plausible. The event must be pharmacologically or phenomenologically definitive, with use of a satisfactory rechallenge procedure if necessary.

- **Probably Related** There is evidence to suggest a causal relationship, and the influence of other factors is unlikely. The clinical event, including an abnormal laboratory test result, occurs within a reasonable time after administration of the study intervention, is unlikely to be attributed to concurrent disease or other drugs or chemicals, and follows a clinically reasonable response on withdrawal (dechallenge). Rechallenge information is not required to fulfill this definition.
- **Potentially Related** There is some evidence to suggest a causal relationship (e.g., the event occurred within a reasonable time after administration of the trial medication). However, other factors may have contributed to the event (e.g., the participant's clinical condition, other concomitant events). Although an AE may rate only as "possibly related" soon after discovery, it can be flagged as requiring more information and later be upgraded to "probably related" or "definitely related", as appropriate.
- Unlikely to be related A clinical event, including an abnormal laboratory test result, whose temporal relationship to study intervention administration makes a causal relationship improbable (e.g., the event did not occur within a reasonable time after administration of the study intervention) and in which other drugs or chemicals or underlying disease provides plausible explanations (e.g., the participant's clinical condition, other concomitant treatments).
- Not Related The AE is completely independent of study intervention administration, and/or evidence exists that the event is definitely related to another etiology. There must be an alternative, definitive etiology documented by the clinician.

8.3.2.3 EXPECTEDNESS

Some of the expected adverse events are: application site discomfort, application site irritation/redness, local pain, face/head/neck area (including toothache), muscle twitching and/or contractions, face/head/neck area (including facial droop and/or lip pull), headache/migraine, dizziness, tingling, pricking, or a feeling of "pins and needles" on the skin where the device is applied (paresthesia/dysesthesia)

Additional expected adverse events, which have been associated with other VNS devices, are cough, gastrointestinal discomfort, hoarseness or change in voice, irregular heart beat (arrhythmia), metallic taste, nausea, shortness of breath (dyspnea)

The principle investigator will be responsible for determining whether an adverse event (AE) is expected or unexpected. An AE will be considered unexpected if the nature, severity, or frequency of the event is not consistent with the risk information previously described for the study intervention.

8.3.3 TIME PERIOD AND FREQUENCY FOR EVENT ASSESSMENT AND FOLLOW-UP

The occurrence of an adverse event (AE) or serious adverse event (SAE) may arise at any time. As a result, the patient will be evaluated directly after each stimulation. The neurointensivist in charge will determine the frequency of vital signs and neurologic examination checks.

All AEs including local and systemic reactions not meeting the criteria for SAEs will be captured on the appropriate case report form (CRF). Information to be collected includes event description, time of onset, clinician's assessment of severity and relatedness to the study device, and time of resolution/stabilization of the event. All AEs occurring while in the study must be documented appropriately regardless of the relationship to the device. All AEs will be followed to adequate resolution.

Any medical condition that is present at the time that the participant is screened will be considered as baseline and not reported as an AE. However, if the study participant's condition deteriorates at any time during the study, it will be recorded as an AE.

Changes in the severity of an AE will be documented to allow an assessment of the duration of the event at each level of severity to be performed. AEs characterized as intermittent require documentation of onset and duration of each episode.

The principal investigators will record all reportable events with start dates occurring any time after informed consent is obtained until 3 days after the last day of study participation (Vagus nerve is stimulated), or until discharge from hospital (whatever comes first). Events will be followed for outcome information until resolution or stabilization.

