4.4 END OF STUDY DEFINITION

The study intervention will be up to 10 days in length. Vagus stimulation will be performed 4 times daily (approximately at 6:30AM, 11:30AM, 4:30PM and 9:30PM). Data collection will continue till hospital discharge. If the participant becomes hemodynamically unstable, defined as hypotension requiring vasopressors the VNS will be held for safety purposes. However, it will be resumed, once the patient is stabilized, off vasopressors for 48 hours. If the patient is being hemodynamically augmented for symptomatic vasospasm, n-VNS will not be withheld as the beneficial effects of n-VNS on symptomatic vasospasm will be investigated in this study.

Participants must fulfill all of the inclusion criteria in order to be eligible for the study:

- Established signed and dated informed consent form
- Can be enrolled within 5 days of cerebral aneurysm treatment.
- CT of the head revealing blood in the subarachnoid space
- Subject has ruptured cerebral aneurysm or SAH patients who do not have vascular malformation on cerebral angiogram.
- Subject is male or female 18 -75 years of age
- Subject is alert able to verbalize pain at the time of enrollment
- Subject reports pain of 7 and greater on a 10 Point Pain numeric rating scale or presenting with severe headache.
- Female of reproductive age must have a negative pregnancy test (Urine or blood test)

nVNS will only be performed if vital signs are stable (HR>60, SBP> 100 mmHg, MAP> 60 mmhg, and saturation > 90% on room, nasal cannula or face mask). Then the vagus nerve will be stimulated.

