7 STUDY INTERVENTION DISCONTINUATION AND PARTICIPANT DISCONTINUATION/WITHDRAWAL

7.1 DISCONTINUATION OF STUDY INTERVENTION

The study intervention will be held during procedure days, or if the participant gets intubated, or is in shock (cardiogenic, distributive or septic). During non-procedure days, or once extubated and stabilized and participant becomes alert the study intervention can be resumed.

In addition, as stated earlier, if HR< 60 beats/min, SBP<100 mm HG, or MAP< 60 mm HG and oxygen saturation < 90 %, the intervention will be postponed.

If hemodynamic instability or unstable arrhythmia occur during the VNS, and is thought to be due to the VNS by the investigator, the participant will be discontinued from the study procedure, however, will be followed until discharge from the hospital.

If a clinically significant finding is identified (including, but not limited to changes from baseline) after enrollment, the investigator or qualified designee will determine if any change in participant management is needed. Any new clinically relevant finding will be reported as an adverse event (AE).

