8.3.5 SERIOUS ADVERSE EVENT REPORTING

The study clinician will report to the IRB any serious adverse event related or potentially related to the study intervention. All serious adverse events (SAEs) will be followed until satisfactory resolution or until the site investigator deems the event to be chronic or the participant is stable.

POTENTIAL SERIOUS ADVERSE EVENT mentioned in section 8.3.2

Monitoring: Participants will be on continuous telemetry recording continuously the EKG, respiratory rate, oxygen saturation, Blood pressure will be recorded one-hour post-stimulation and 1-4 hours afterwards. Vital signs will be recorded before and directly after stimulation, the medical professional will be at bedside during the stimulation monitoring any side effect. Vital signs and neurologic examination are evaluated every 1-4 hours and as needed afterwards. The VNS will be performed in the intensive care unit setting, where personnel are trained in cardiopulmonary resuscitation and treating hemodynamically unstable patients.

Actions:

- Participants must have stable vital signs (SBP> 100mmHg, MAP>60 mmHg, HR> 60 beats/minute, oxygen saturation > 90%, not on mechanical ventilation) before the vagus nerve is stimulated. If unstable vital signs, the stimulation will be skipped, until the patient is more stable.
- If the participants develop a life-threatening arrhythmia thought to be due to the VNS, subject will be taken off therapy, but will continue to be followed until end of study.
- If the participants get intubated or develops hemodynamic shock due to the natural history of the disease, the subject will be taken off the therapy.

The study investigator shall complete an Unanticipated Adverse Device Effect Form and submit to the reviewing Institutional Review Board (IRB) as soon as possible, but in no event later than 7 working days after the investigator first learns of the effect. The principle investigator is responsible for conducting and evaluating any unanticipated adverse device effect and shall report the results of such evaluation to the reviewing IRB and participating investigators within 7 working days of the event.

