The primary efficacy variable, the daily morphine equivalency dose by visit, will be analyzed using a restricted maximum likelihood (REML)-based repeated measures approach (Mixed Model Repeated Measures (MMRM)). The model for analysis will include fixed, categorical effects of treatment, visit, and treatment by visit interaction, as well as the continuous, fixed covariates of baseline value. An unstructured (co)variance structure will be used to model the within-patient errors. If this analysis fails to converge, compound symmetry will be tested. The (co)variance structure converging to the best fit, as determined by Akaike's information criterion will be used as the primary analysis. The Kenward-Roger approximation will be used to estimate denominator degrees of freedom. The primary treatment comparison will be the contrast between treatments at Day 14 for active treatment versus sham treatment. Treatment group differences contrasts will be computed overall and for each analysis visit (i.e., Day 1, Day 2, Day 3, ..., Day 14) and displayed with the respective 95% CIs. Significance tests will be based on least-squares means and Type III sum-of-squares, using two-sided tests at the 0.05 level (two-sided 95% confidence intervals). No imputed values will be used for the MMRM analysis.

Sensitivity analysis

All analyses on the primary efficacy endpoint will be repeated on the PPS

Additionally, the missing data for the mean daily morphine equivalency dose will be computed using an LOCF algorithm and analyzed using the MMREM model.

Analysis of Secondary and Exploratory Variables

For each of the variables mentioned above, the randomization group difference will be examined using a T-test for continuous variables, and Fisher's exact test for categorical variables at each visit.

Analysis of safety variables

Treatment group differences in the occurrence of serious adverse events will be evaluated using Fisher's exact test.

Adverse events:

The primary safety endpoint of this study is the overall incidence of device related serious AEs. AEs and SAEs will be summarized and presented as proportions and respective 95% exact binomial confidence intervals (CIs).

Frequency and percentage of subjects experiencing a specific adverse event will be tabulated by system organ class, preferred term, and treatment group.

Summary tables and subject data listings will be provided.

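### Protocol section 8.3.3 stops recording new adverse events 3 days after the last stimulation, while sections 4.4, 7.1 and 8.3.5 follow patients longer, so safety observation depends on exposure

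*Protocol*

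**What the plan says.** Protocol section 8.3.3 opens the recording window for reportable events at consent ("start dates occurring any time after informed consent is obtained") and closes it "until 3 days after the last day of study participation (Vagus nerve is stimulated), or until discharge from hospital (whatever comes first". The first parenthesis equates the last day of participation with the last stimulation. The same section also says "All AEs occurring while in the study must be documented appropriately regardless of the relationship to the device", and asks that events be followed to resolution. It gives no other closing date for events that have not yet begun.

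Other sections run longer. Section 4.4 says "The study intervention will be up to 10 days in length", but also "Data collection will continue till hospital discharge". For instability or arrhythmia attributed to the device, section 7.1 says "the participant will be discontinued from the study procedure, however, will be followed until discharge from the hospital". For a life-threatening arrhythmia attributed to the device, section 8.3.5 says "subject will be taken off therapy, but will continue to be followed until end of study". Section 8.3.5 gives no period for new events in patients taken off for intubation or shock. Section 7.2 gives none for patients withdrawn by the investigator.

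The SAP sets no adverse event window. Its safety set is every randomised patient with at least one stimulation, so early stoppers stay in. Under the analysis of safety variables it says "Treatment group differences in the occurrence of serious adverse events will be evaluated using Fisher's exact test". It presents adverse events as proportions with exact confidence intervals, and names device-related serious events as the primary safety endpoint. No time at risk is planned.

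**The concern.** Safety is a primary objective, and the protocol states that the risks of nVNS in this population are unknown. Under section 8.3.3 the length of safety observation is set partly by the treatment: a patient who stops stimulation early is covered for fewer days than one who completes. Staff who follow section 8.3.3 and staff who follow sections 4.4 or 7.1 would record different events for the same patient.

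Two kinds of information can be lost: later serious events in any stopped patient, and all later events in patients stopped for non-serious harm or for reasons unrelated to the device. Section 8.3.2.1 lists treated hypotension and haemodynamically stable arrhythmia as severe, and notes that severe is not the same as serious. A patient stopped for one of these may therefore have no serious event on record when the window closes. If such stops were more common in one arm, the recorded all-cause proportions would not be comparable.

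**Working it through.** The plan gives no serious event rate, stopping rate or power figure, so there is nothing of its own to reproduce.

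**1. The end of observation, section by section**

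| Place | Who | Until when |
|---|---|---|
| 8.3.3 | everyone, new reportable events | last stimulation + 3 days, or discharge if sooner |
| 4.4 | everyone, data in general | discharge |
| 7.1 | stopped for device-attributed instability or arrhythmia | discharge |
| 8.3.5 | stopped for device-attributed life-threatening arrhythmia | end of study |
| 8.3.5 | taken off for intubation or shock | not stated |
| 7.2 | withdrawn by the investigator | not stated |

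Sections 4.4, 7.1 and 8.3.5 do not say that new events are recorded after the 8.3.3 limit, and 8.3.3 makes no exception for them. For the last two rows, only the general sentence in 4.4 competes with 8.3.3.

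**2. Window length**

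Day 1 is the first stimulation day, and the patient is still in hospital. Window = last stimulation day + 3.

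- Day 1: 4 days
- Day 2: 5 days
- Day 5: 8 days
- Day 10: 13 days, the maximum

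**3. Effect on the serious event comparison if stopping differs by arm**

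Assumptions, none from the documents: no device effect; a constant daily hazard h of a first serious event; 20% of the active arm and none of the sham arm last stimulated on day 2; stops unrelated to a serious event; no early discharge. Twenty per arm follows from about 40 patients at 1:1.

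P(recorded event) = 1 − exp(−h × window). At h = 0.02:

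- 13 days: 1 − exp(−0.26) = 0.229
- 5 days: 1 − exp(−0.10) = 0.095
- Active: 0.8 × 0.229 + 0.2 × 0.095 = 0.202, or 4.04 patients in 20
- Sham: 0.229, or 4.58 patients in 20
- Gap: 2.7 points, or 0.54 patient

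| h per day (assumed) | Active | Sham | Gap |
|---|---|---|---|
| 0.01 | 10.7% | 12.2% | 1.5 points |
| 0.02 | 20.2% | 22.9% | 2.7 points |
| 0.05 | 42.7% | 47.8% | 5.1 points |

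With 10% to 30% of the active arm stopping on day 2, over these hazards, the gap runs from 0.7 to 7.7 points. With a common 13-day window it is zero.

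If the active arm truly had twice the hazard, the same 20% stopping pattern would lower the power of the two-sided Fisher test at 0.05 from 14.8% to 9.0% (sham h = 0.02), or from 25.7% to 12.9% (sham h = 0.05). Power is low either way.

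**4. If the stops are themselves serious events**

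Each such patient already counts once in the proportion. At h = 0.02, active becomes 0.20 + 0.80 × 0.229 = 0.383 against 0.229 for sham. The active arm then looks worse, and the shortened window removes none of these patients from the count.

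**5. What days at risk would show**

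In step 3 the arms have 16 × 13 + 4 × 5 = 228 and 20 × 13 = 260 patient-days. At h = 0.02 the rates are 4.04/228 = 0.0177 and 4.58/260 = 0.0176 per patient-day, so the apparent difference almost disappears.

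**The case against.** The strongest reply is that the protocol already protects the patients who matter most. Those stopped for a device-attributed arrhythmia or instability are followed to discharge (7.1) or to end of study (8.3.5). Section 8.3.3 itself wants every event during the study documented, section 8.3.4 collects events of the disease's natural history as secondary endpoints, and section 4.4 collects data to discharge. On that reading the 3-day limit governs only reportable events and little is lost.

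The primary safety endpoint is also well matched to a short tail. The relatedness categories in section 8.3.2.2 depend on plausible timing. Section 8.4.3 expects most side effects during stimulation and allows 3 days to judge whether a problem is due to the device.

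Much of this stands. It limits the damage, and it means that loss of events is possible rather than established. It does not remove the contradiction, because none of these provisions states that a new event beyond the 8.3.3 limit is recorded. Nor does it help patients withdrawn under section 7.2 or taken off for intubation or shock, beyond the general sentence in 4.4.

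Three stronger readings are tempting, and the documents do not support them:

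- A reader might infer that Fisher's test is invalid because it needs equal observation time. It does not. Unequal individual windows bias the comparison only if their distribution differs by arm.
- A reader might infer that the plan generally favours the device. That requires more early stopping on active, for reasons other than a serious event. The documents predict no such difference, and step 4 shows the direction can reverse.
- A reader might infer that patients harmed by the device drop out of the safety result. A patient stopped by a serious event is already counted. Nor do early stoppers always have the shortest window, since early discharge can shorten it further.

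**Conclusion.** The concern holds as a contradiction on when adverse event recording ends, with a treatment-dependent window as its consequence. The window lengths (5 days against 13 for last stimulations on day 2 and day 10) follow directly from section 8.3.3, before any earlier discharge.

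Bias in the all-cause serious event comparison is conditional on early stopping that differs by arm. Its illustrated size is modest: 2.7 points, about half a patient in 20, under the assumed hazard and stopping rates. The device-related endpoint is less exposed. Confidence is high on the contradiction and the unequal windows, and lower on whether any bias would arise or in which direction. The change is worth making because the clash is plain and cheap to remove, in a study whose safety question is open.

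**What to change.** **Protocol.** Reconcile sections 4.4, 7.1, 8.3.3 and 8.3.5 on one end of recording. New adverse events and serious adverse events should be recorded from consent to hospital discharge for every randomised patient, whether or when stimulation stopped and whatever the reason. That also covers the patients for whom sections 7.2 and 8.3.5 give no period. Keep the interval of 3 days after the last stimulation only as a flag for on-treatment events. Sections 7.1 and 8.3.5 also differ on whether stimulation is held or ended after intubation or shock, and must be reconciled. With recording to discharge, the safety window no longer depends on the answer.

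**SAP.** State that window for the serious event analyses. Discharge times also differ (section 8.1 gives NSCU stays of 2 to 21 days), so recording to discharge does not by itself equalise observation. Report patient-days at risk and serious event rates per patient-day by arm beside Fisher's test. Treat the rates as descriptive, since risk after SAH need not be constant over the stay.

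**Cost.** About one sentence in section 8.3.3, aligned wording in the other sections, and a line or two in the SAP. No visits are added, because patients are in hospital and section 4.4 already collects data to discharge. The downside is more disease-related events to log and assess.

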8.3.4 ADVERSE EVENT REPORTING

Given that patients with SAH experience many known complications, like hydrocephalus, strokes, delayed cerebral ischemia, cerebral vasospasm, fever, electrolyte disturbance, post-operative complications, only adverse effects that are thought to be related to the study device or are unexpected as part of the natural course of subarachnoid hemorrhage will be reported. The Neurointensivist in charge of the patient will evaluate all side effects and deem its seriousness and relatedness to the device.

All adverse effects thought to be part of the natural history of SAH, or mild side effects that are expected to occur during the VNS such as skin irritation, muscle twitch, transient dyspnea during stimulation, transient hoarseness during stimulation, mild pain at the stimulation site will be recorded in the participant's medical record and will be collected as secondary endpoints. All serious or severe or unexpected side effects related to the device will be reported to the IRB within 7 days of the PI's knowledge. Any unknown adverse event thought to be related to the device will also be reported to the IRB.
Adverse Events reporting:

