8.2 SAFETY AND OTHER ASSESSMENTS

nVNS has been proven to be safe. However, the risks of VNS in SAH population are not known. In order to minimize the risks, if an aneurysm has been identified to be the cause of the SAH, patients will only be enrolled if the aneurysm has been completely treated. This information will be pulled from the medical record. Past medical and surgical history, respiratory and hemodynamic state will be pulled from the medical record. Vital signs and neurologic examinations are usually performed every 1 to 4 hours depending on the acuity of each case, and pain assessment evaluated every 4 hours and as needed. In the NSCU, patients are on continuous ECG analyzes via telemetry. Stimulation will only be given if HR >60 and the SBP>100 mmHg, MAP> 60 mmHg and oxygen saturation is >90% for safety concerns. The presence of intolerable pain at the stimulation site, skin irritation, hoarseness, and change in the taste, shortness of breath, chest pain, nausea, and vomiting will be evaluated.

Safety outcomes:

- Rate of Symptomatic bradycardia defined as a drop in HR to less than 60 beats per minutes with symptoms, not due to nimodipine. The timing of nimodipine relative to the VNS will be recorded. All patients are on telemetry during the stimulation.
- Rate of drop in blood pressure, defined as a drop in blood pressure requiring fluid resuscitation or vasopressor support thought to be due to the device.
- Rate of side effects: presence of intolerable pain at the stimulation site, skin irritation, nasopharyngitis, hoarseness, dysgeusia, shortness of breath, chest pain, nausea and vomiting.

Figure

Days 1-3	Screening			
 Total n=40 Obtain informed consent Screen potential participants by inclusion and exclusion criteria Obtain history, document Randomize 				
Days 2-4 till discha from ICU	rge Baseline assessments/ Study Intervention			
 Obtain daily cumul Evaluate presence Evaluate seizures d Complete vital sign Questionaire for sign 	as before and after each stimulation and daily trend de effects from VNS post every stimulation scranial dopplers (TCD) comatic vasospaspm I fever			
Discharge from the hospital or day 10 post-ictus				

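### The Protocol's adverse event rules conflict on whether SAH complications are recorded as AEs, and the SAP's by-arm SAE test does not say which rule supplies its data

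*Protocol*

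**What the plan says.** **Protocol 8.3.3** sets a broad rule: "All AEs occurring while in the study must be documented appropriately regardless of the relationship to the device". It adds that "if the study participant's condition deteriorates at any time during the study, it will be recorded as an AE". Its sentence on the CRF covers AEs that do not meet the SAE criteria. Its closing paragraph has the principal investigators record all *reportable* events within a time window, which ties recording to reportability.

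**Protocol 8.3.4** first names known SAH complications: hydrocephalus, stroke, DCI, vasospasm, fever, electrolyte disturbance and post-operative complications. It then says that "only adverse effects that are thought to be related to the study device or are unexpected as part of the natural course" of SAH will be reported. The treating neurointensivist judges seriousness and relatedness. "All adverse effects thought to be part of the natural history of SAH", together with mild expected device effects, "will be recorded in the participant's medical record and will be collected as secondary endpoints".

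**Protocol 11.1.4.1**, under a heading that marks it as a possible alternative AE section, requires all AEs to be recorded on the CRF.

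**SAP, Analysis of safety variables:** "Treatment group differences in the occurrence of serious adverse events will be evaluated using" Fisher's exact test. The test is not limited to device-related events. The primary safety endpoint is limited in that way.

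**Oversight.** Under Protocol 10.1.6 an unblinded co-investigator reviews aggregate safety data weekly. Under 10.1.7 an unblinded investigator reviews unexpected or serious events.

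**The concern.** The Protocol itself says of this population: "However, the risks of VNS in SAH population are not known". When device risk is unknown, the informative safety comparison is all SAEs by randomized arm, because it does not need anyone to decide correctly which events the device caused. The SAP plans that comparison, but the Protocol does not secure the data for it. A clinician who follows 8.3.4 can classify a serious event as natural to SAH and leave it off the AE record. Another who follows 8.3.3 or 11.1.4.1 would enter it. The SAE table, the Fisher test and the material that reaches the unblinded reviewers would then depend on which section was followed.

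**Working it through.** The plan gives no SAE rate, power or margin, so there is no figure of its own to reproduce. The main check is a comparison of the text; the arithmetic is illustrative.

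**1. Do the rules agree?**

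| Source | Which events | Where they go |
|---|---|---|
| 8.3.3 | All AEs, any attribution | Documented; CRF named only for AEs that are not SAEs |
| 8.3.3, last paragraph | Reportable events | Recorded by the principal investigators |
| 8.3.4 | Device-related, or unexpected in SAH | Reported; recipient not named in that sentence |
| 8.3.4 | Natural history of SAH; mild expected device effects | Medical record and secondary endpoints |
| 8.3.5 | Related or potentially related SAEs | IRB |
| 11.1.4.1 (possible alternative) | All AEs | CRF |

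They do not agree. Mild device effects are non-serious AEs, so 8.3.3 sends them to the CRF while 8.3.4 sends them to the chart and secondary endpoints. For SAEs, only the unadopted alternative text clearly puts every event on the CRF.

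**2. Do other outcomes cover the gap?** In part.
- Stroke, DCI, vasospasm, seizure and central fever are exploratory outcomes in Protocol section 3 and the SAP. They need no judgement of device causality, and the SAP tests categorical ones by arm with Fisher's exact test.
- They appear in neither document's list of secondary endpoints, so the promise in 8.3.4 is not carried through.
- The SAP names no population for exploratory variables. It analyzes them in the same section as the secondary variables, which use mITT only. mITT needs at least 7 days of treatment; if it applies, a patient who dies or stops earlier is excluded. The safety set needs only one stimulation.
- Hydrocephalus and post-operative complications, both on the 8.3.4 list, have no separate SAP outcome. Nor has all-cause death. Death is an SAE criterion in 8.3.2; otherwise it could show only through the modified Rankin scale, a Protocol secondary endpoint that the SAP omits.

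**3. How much could undercounting matter?**
Inputs from the SAP: about 40 patients, equal allocation (40 / 2 = 20 per arm), two-sided 0.05. Assumptions: true SAE rates p1 and p2, and a share c of SAEs that reaches the dataset.

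Power = sum over a, b of Bin(a; 20, c·p1) × Bin(b; 20, c·p2), taken over pairs (a, b) with Fisher p ≤ 0.05.

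| Assumed true rates | c = 100% | 75% | 50% | 25% |
|---|---|---|---|---|
| 60% v 20% | 65% | 44% | 24% | 7% |
| 50% v 20% | 41% | 26% | 14% | 4% |
| 40% v 10% | 49% | 33% | 17% | 3% |

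In counts for the first row: 20 × 0.60 = 12 and 20 × 0.20 = 4 give p = 0.022. At half capture, 6 v 2 gives p = 0.24.

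**4. Does the loss create a false difference?** Take a true rate of 50% in both arms. With equal capture the false-positive rate stays near 2% (2.0% at full capture, 2.4% at half). With unequal capture it rises: 8% at 75% v 50%, and 27% at 100% v 50%.

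**The case against.** The strongest reply is that 8.3.4 concerns reporting and 8.3.3 concerns capture. Section 8.3.4 is headed as reporting, the only recipient it names is the IRB, and 8.3.5 also deals with the IRB. On that reading there are two tiers and no conflict. The section also ends in a sub-heading with nothing under it in the available text, so a table may be missing. This reading is possible but not secure. The limiting sentence names no recipient, 8.3.3 ties recording to reportable events, and 7.1 uses the same verb for entering a finding as an AE.

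Other parts of the defence stand:

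- A reader might infer that natural-history events exist only in the chart, or that an excess of stroke or DCI on active would be invisible. The documents do not support this. Section 8.3.4 adds collection as secondary endpoints, and both documents compare stroke and DCI by arm. What such events can be missing from is the SAE table, the SAE test and the safety review.
- A reader might infer that deaths are routed away. No section says so: death is an SAE, and 8.3.5 follows all SAEs. The weakness is that death has no second route into the SAP.
- A reader might infer bias between arms. Protocol 6.3 blinds the AE assessor, so loss should be about equal while blinding holds.
- A reader might infer that one lost event hides a signal. That is true only at a boundary: 5 v 0 gives p = 0.047 and 4 v 0 gives 0.106. But 6 v 0 gives 0.020, and with background events 12 v 4 (0.022) and 11 v 4 (0.048) both stay below 0.05.
- The weekly unblinded review in 10.1.6 is not limited to unexpected or serious events. It can still see only what was captured as safety data.

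**Conclusion.** The point holds as a conflict between stated rules and an undefined source for a planned test. SAEs judged natural to SAH can drop out of the SAP's between-arm comparison and of the unblinded review. The gap is largest for all-cause death, hydrocephalus and post-operative complications. It is smaller for stroke, DCI, vasospasm, seizure and central fever, whose by-arm comparison remains but has no stated population.

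The expected harm is undercounting and lost sensitivity. Under the assumed rates, losing half of the SAEs equally in both arms removes more than half of the power of a test that is weak even with full capture. The rates and capture shares are assumptions, and the trial is a pilot with no formal hypothesis, so these figures show direction and rough scale only. Bias between arms would need capture to differ by arm, for example through failed blinding.

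**What to change.** 1. In 8.3.4, state that the attribution limit applies only to IRB reporting, and bring the reportable-events sentence in 8.3.3 into line.
2. State once that all AEs and SAEs, including SAH complications and deaths, go on the CRF regardless of judged cause, and are given by arm to the unblinded reviewer.
3. Adopt section 11.1 or delete it.
4. In 8.3.4, replace the reference to secondary endpoints with the outcomes meant, and name the analysis population for the exploratory variables in the SAP.
5. In the SAP, name the source of the SAE data. Tabulate and compare all-cause SAEs and all-cause deaths by arm in the safety set, beside device-related SAEs.

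The cost is a few sentences in each document and more CRF entries for events already in the chart. Sample size and the primary endpoints do not change.
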